The treatment variable was exposure to the BCC intervention (yes/no). The covariates included physical activity, obesity, dietary habits, lifestyle factors, and socio-demographic characteristics. Physical activity was classified according to WHO guidelines (7) as: (i) sedentary: light-intensity activities; (ii) active: moderate-intensity activities for 150–300 minutes per week; and (iii) athlete: vigorous-intensity activities for 75–150 minutes per week. Obesity was assessed using body mass index (BMI, kg/m²) and categorized according to WHO Asian-specific cut-offs (8): (i) underweight (<18.5), (ii) normal weight (18.5–22.9), (iii) overweight (23.0–27.5), and (iv) obese (>27.5). Dietary information was collected using a five-day 24-hour recall method, and dietary diversity score (DDS) was calculated following FAO guidelines (9) . Lifestyle-related covariates included food cravings for high-fat or sweet foods (10), skipping breakfast, sleep duration, bedtime and caffeine intake (11). Socio-demographic variables included family history of menstrual disorders, age at menarche, marital status, and participants' residence as well as parental educational and occupational status.

Data were collected through interviewer-administered, culturally adapted, and validated Bengali-questionnaires. Descriptive statistics summarized baseline characteristics. Group differences were tested using chi-square and t-tests. Propensity scores were estimated using logistic regression, and covariate balance post-matching was evaluated using standardized mean differences (SMD <10%). Intervention effects were analyzed using conditional logistic regression on the matched sample, and logistic regression (bivariate/multivariate) on the unmatched sample. Sensitivity analyses included covariate balance diagnostics, estimation of average treatment effects (ATE/ATT), and Bayesian logistic regression with log Bayes factor.

This study complies with U.S. regulatory requirements for clinical trial registration and reporting under 42 CFR Part 11. The responsible party confirms that all submitted information is complete and accurate, and that the study protocol, statistical analysis plan (SAP), and informed consent form (ICF) reflect the approved trial objectives and design.

Participant flow

Recruitment details

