Female students were recruited from three public universities in Bangladesh: Patuakhali Science and Technology University (PSTU), Barisal University (BU), and Khulna University (KU) for a BCC module on menstrual health from May 20 to June 30, 2023. Recruitment occurred via campus outreach and voluntary registration. University-approved session dates were held in campus venues. Follow-up occurred from July 15, 2023, to January 15, 2024. A post-intervention assessment was conducted from February to March 2024 through comparing the intervention group to the control group.

Pre-assignment details

Initially 498 participants (249/group) were recruited. Seven intervention participants were excluded before assignment for missing sessions/protocol violation, leaving 242. At six-month follow-up, 480 participants (239 intervention, 241 control) completed assessments as because 3 intervention and 8 control participants were excluded due to missed follow-up or withdrawal. After data checks, 8 were excluded for invalid dysmenorrhea data, leaving 234 intervention and 238 control (total 472 participants) for that outcome. For PMS and MI, 24 more were excluded (10

intervention and 14 control group), yielding 456 participants (228 per group). Propensity score matching (PSM) identified 196 matched participants (98 per group) for each of outcomes.

Group information

Two groups were assigned: an intervention group receiving the BCC module on menstrual health, and a control group with no intervention. Participants were female university students from PSTU, BU, and KU, Bangladesh, with group assignment based on attending at the BCC sessions.

Group title

1. Intervention Group
2. Control Group

Group description

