The Intervention group comprised female university students from PSTU, BU, and KU who participated in a structured BCC module designed to enhance awareness and promote effective management of menstrual disorders through lifestyle and behavioral modifications. The module consisted of three interactive sessions that included educational presentations, yoga demonstrations, informational pamphlet distribution, quiz competitions, and small gift incentives to boost engagement. Sessions were facilitated by trained female educators under the guidance of a public health expert and a gynecologist. Participants were selected through voluntary registration and received follow-up support at every two months to reinforce behavioral changes, address challenges, and ensure continued adherence to healthy practices.

The Control group consisted of female students from the same universities who were not exposed to the BCC intervention. They were selected using student dormitory records and matched to the intervention group through propensity score matching to ensure comparability. As they did not receive any form of menstrual health education or BCC intervention, this group served as the baseline comparator for evaluating the effectiveness of the BCC module on menstrual health outcomes.

Period(s)

This study was organized into three distinct periods to reflect the logical progression of the intervention and its evaluation: (1) implementation of the intervention, (2) follow-up phase to monitor and support behavior change, and (3) post-intervention evaluation to assess outcomes. Each period captured critical milestones and participant flow to assess the feasibility, adherence, and effectiveness of the intervention.

Period 1: Implementation of the intervention

The first period of the study involved the implementation of a structured BCC intervention among female university students to enhance awareness and promote effective management of menstrual disorders. Three structured sessions were conducted covering menstrual disorders, dietary behaviors, and physical activity. Two trained female educators facilitated these sessions. The details of participation status of this period is presented in Table 1.

Table 1. Summary of participation status and key milestones in intervention implementation

Participation status	Data (number of participants)	Comments	Milestone title	Milestone data (number of participants)

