To evaluate the impact of the BCC intervention on reducing dysmenorrhea, key covariates were balanced between groups using propensity score matching. These included physical activity level, BMI, minimum dietary diversity (MDD score ≥ 5), food cravings for high-fat and sweet foods, breakfast skipping, sleep duration, caffeine intake frequency, family history of menstrual disorders, age at menarche, marital status, father's and mother's educational status, and mother's occupation. These balanced covariates (13 covariates) were included in the regression models and in the estimation of both the average treatment effect (ATE) and the average treatment effect on the treated (ATT).

Additionally, to assess the effectiveness of the intervention on PMS and MI outcomes, propensity score matching was used to achieve balance in key baseline covariates between the intervention and control groups. The matched covariates included physical activity level, BMI (kg/m^2), minimum dietary diversity (MDD score ≥ 5), food cravings for high-fat and sweet foods, breakfast skipping, sleep duration, age at menarche, and participants' residence. These variables (8 covariates) were subsequently adjusted for in the estimation of treatment effects.

Table 6. Baseline characteristics of participants by defined study measures

Baseline measure title (Study-specific measure)	Study-specific baseline measure title(s)	Baseline measure description	Measure type	Measure of dispersion	Category title	Unit of measure
Physical activity	Physical activity level	Categorized per WHO recommendations based on weekly activity intensity: sedentary (with little or no activity), active (moderate, 150–300 min/week) and athlete (vigorous, 75–150 min/week). Active and athlete were merged during analysis	Count of participants	Not applicable	Sedentary/ Active and athlete	Participants
Body mass index (BMI)	BMI (Kg/m ²)	Classified using WHO cut-offs for Asian populations, such as underweight (<18.5), normal (18.5–22.9) and overweight/obese (≥23.0). Overweight and obese categories were merged.	Count of Participants	Not applicable	Underweight / Normal / Overweight and obese	Participants

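### University is in neither propensity model nor any described outcome model, and the campus mix by arm is not reported, so confounding by campus is neither removed nor ruled out.

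*Combined protocol and SAP*

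**What the plan says.** **Sites and routes into the arms.** "Female students were recruited from three public universities in Bangladesh" (Recruitment details). Delivery was on campus: "University-approved session dates were held in campus venues". Women were not randomised; the Group information section defines the arms "with group assignment based on attending at the BCC sessions". Intervention women registered voluntarily. For the comparison arm the Group description says: "The Control group consisted of female students from the same universities who were not exposed to the BCC intervention", and "They were selected using student dormitory records and matched to the intervention group through propensity score matching to ensure comparability". No campus quota or count is stated for either arm.

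**Covariates.** The Detailed description lists the background variables: "Socio-demographic variables included family history of menstrual disorders, age at menarche, marital status, and participants' residence as well as parental educational and occupational status". Baseline Measure Information then gives two matching sets.

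- Dysmenorrhea: physical activity, BMI, dietary diversity, cravings, breakfast skipping, sleep, caffeine, family history, age at menarche, marital status, father's education, mother's education, mother's occupation. "These balanced covariates (13 covariates) were included in the regression models".
- PMS and MI: "The matched covariates included physical activity level, BMI (kg/m^2), minimum dietary diversity", followed by cravings, breakfast skipping, sleep, age at menarche and residence, 8 in all.

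University is in neither set, and it is absent from Table 6 and Tables 7A and 7B. Residence is not a substitute: Table 6 defines it as living with family or in a dormitory.

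**Analysis.** The SAP describes 1:1 nearest-neighbour matching (caliper 0.01, no replacement), conditional logistic regression on the pairs, and logistic regression on the unmatched data. It mentions no within-campus restriction, university term or campus-stratified estimate.

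**The concern.** University was fixed before the sessions and should already be on file, since recruitment was organised by campus. That makes it unusually useful here. Baseline Measure Data states that the covariates were measured at outcome evaluation, so activity, diet, BMI, sleep and cravings may already reflect the intervention. University cannot.

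The different recruitment routes are a reason not to take an equal campus mix for granted. The full samples differ clearly even on traits that the sessions could not alter (Table 7A, intervention against control):

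- mean age at menarche 13.4 against 12.1 years;
- father's education below secondary in 17/234 (7%) against 50/238 (21%).

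These traits say nothing directly about campus, but they show that the routes drew different women. If one campus has a higher prevalence of menstrual disorders and supplies a larger share of controls than of treated women, part of that difference is counted as intervention effect in every primary estimate. Without campus counts a reader cannot tell whether this happened.

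**Working it through.** **1. Is university in any model?** The check was made against both matching sets, the general covariate list, Tables 6, 7A and 7B, and the SAP. It is in none of them.

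**2. How far apart are the recruited samples on fixed traits?** Standardised difference in age at menarche, from the means and SDs in Table 7A: (13.4 - 12.1) / sqrt((1.5² + 1.7²)/2) = 1.3 / 1.60 = 0.81. This is before matching, and menarche is then matched on. University is not, so no corresponding check exists for it.

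**3. How could pairs fall across campuses?** Assume that each campus supplies one third of each arm and is unrelated to the propensity score. Then about 98/3 ≈ 33 of 98 pairs would be within one campus by chance. With equal mix, cross-campus pairs do not bias the estimate (step 5).

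**4. Bias on the risk-difference scale.** For a two-type campus contrast with no other adjustment:

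bias = (difference in campus share between arms) × (difference in prevalence between campuses).

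Both inputs are assumptions, because the documents give neither.

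- 0.20 × 0.20 = 0.04
- 0.40 × 0.30 = 0.12

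The table shifts the Table 12 estimates by these amounts, in the direction that would have favoured the intervention and keeping the interval widths.

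| Outcome | Estimate | Table 12 | Less 4 points | Less 12 points |
|---|---|---|---|---|
| Dysmenorrhea | ATT | -0.27 (-0.40, -0.13) | -0.23 (-0.36, -0.09) | -0.15 (-0.28, -0.01) |
| PMS | ATT | -0.42 (-0.57, -0.26) | -0.38 (-0.53, -0.22) | -0.30 (-0.45, -0.14) |
| MI | ATT | -0.31 (-0.45, -0.16) | -0.27 (-0.41, -0.12) | -0.19 (-0.33, -0.04) |
| Dysmenorrhea | ATE | -0.23 (-0.35, -0.11) | -0.19 (-0.31, -0.07) | -0.11 (-0.23, +0.01) |

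At 12 points no point estimate changes sign. The dysmenorrhea ATE interval just reaches zero; the ATE intervals for PMS (-0.40, -0.13) and MI (-0.29, -0.06) do not.

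**5. Bias on the odds-ratio scale.** Assume no treatment effect, 40% prevalence at the lower-prevalence campus type, and a given odds ratio between campus types. The spurious OR compares the two mixed prevalences. Example, with a between-campus OR of 2:

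- Higher-campus prevalence: odds 0.667 × 2 = 1.333, so 57.1%.
- Intervention, 20% at the higher campus: 0.20 × 0.571 + 0.80 × 0.40 = 0.434.
- Control, 50% at the higher campus: 0.50 × 0.571 + 0.50 × 0.40 = 0.486.
- Spurious OR: (0.434/0.566) / (0.486/0.514) = 0.81.

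Dividing the matched ORs in Table 11 and their upper limits by the spurious OR gives an approximate correction (a marginal OR applied to a conditional one):

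| Share at higher campus, intervention vs control | Between-campus OR | Spurious OR | Dysmenorrhea 0.13 (upper 0.34) | PMS 0.12 (upper 0.27) | MI 0.21 (upper 0.45) |
|---|---|---|---|---|---|
| equal | any | 1.00 | unchanged | unchanged | unchanged |
| 25% vs 40% | 1.5 | 0.94 | 0.14 (0.36) | 0.13 (0.29) | 0.22 (0.48) |
| 20% vs 50% | 2 | 0.81 | 0.16 (0.42) | 0.15 (0.33) | 0.26 (0.55) |
| 10% vs 60% | 3 | 0.58 | 0.22 (0.58) | 0.21 (0.46) | 0.36 (0.77) |
| 0% vs 100% | 3 | 0.33 | 0.39 (1.02) | 0.36 (0.81) | 0.63 (1.35) |

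Of the scenarios shown, only a complete split of the arms by campus takes an upper limit past 1. Both arms are stated to come from the same three universities, so that row is a bound and not a plausible case.

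**The case against.** The strongest reply is that the omission is a reporting gap and not a demonstrated bias. Both arms came from the same three universities; this is not a design in which whole campuses were treated or untreated. If the mix was similar, campus differences average out over the pairs. That stands, and it limits the conclusion to what has not been removed or excluded.

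Some likely pathways are also partly covered. Dietary diversity, cravings and breakfast skipping are in both sets, and living arrangement is in the PMS and MI set. The formula in step 4 ignores this and treats the whole campus difference as unadjusted, so its results lean high. Against that, most of these covariates were measured after the intervention and are weaker stand-ins for a pre-exposure factor.

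A reader might infer two stronger things that the documents do not support.

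- *That pairing women from different universities is itself a bias.* It is not. Bias needs both a different campus mix by arm and a different outcome risk by campus, and the equal-mix row in step 5 gives a spurious OR of exactly 1.00.
- *That shared session or facilitator effects by campus confound the comparison.* Controls had no sessions, so such effects are part of the treatment or a matter of clustered variance. Matching within campus would not remove them. The description of Period 1 mentions two educators and does not say that they differed by campus.

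**Conclusion.** The omission is certain: university is in neither propensity model, in no described outcome model and in no baseline table, although the arms were recruited differently across three campuses. Whether it biased the results cannot be determined, because the documents give neither the campus mix by arm nor outcomes by campus.

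Under the assumed range the bias is about 4 to 12 points. In the direction favouring the intervention, 12 points would reduce the ATTs from -27, -42 and -31 points to -15, -30 and -19. The effects shrink but do not reverse, and among the intervals in Table 12 only that of the dysmenorrhea ATE would touch zero. An imbalance in the other direction would mean that the effects are understated. All these sizes rest on assumed campus shares and prevalences. The point calls for an inexpensive improvement that should be made; it is not evidence that the reported benefit is due to campus.

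**What to change.** 1. Add university indicators (two, for three campuses) to both propensity models and to the unmatched multivariable models.
2. Adjust for university in the matched conditional logistic model. Pairs that cross campuses differ on it, so matching alone does not remove it within the pair.
3. Report counts by campus and arm before and after matching for each outcome sample, with university in the balance diagnostics, and show the effect by campus descriptively.
4. Repeat the analysis with exact matching within university, as a sensitivity analysis.

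Items 1 to 3 need only a re-analysis with a variable that should already be held, at the cost of two parameters per model. The number of pairs may change a little when the scores are re-estimated.

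Item 4 has a real price. The 0.01 caliper already excludes 136 of 234 treated women for dysmenorrhea (Table 4A) and 130 of 228 for PMS and MI (Table 4B), and splitting the pool by campus makes close matches scarcer. In an illustrative simulation (234 against 238 women, normally distributed scores, about 91 pairs without restriction), exact matching within three campuses left about 73 pairs with equal mix and about 69 with a 20-point difference in mix. The losses are (91 - 73)/91 ≈ 20% and (91 - 69)/91 ≈ 24%. For that reason it should not be the lead remedy.

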Started	249 (Intervention Group) 249 (Control group)	Intervention: participants who registered after informed consent and attended the first session of BCC module Control: Participant from the same universities were selected and listed after providing consent for the assessment study.	Intervention: first session attendance Control: Not exposed to the BCC intervention	249 (Intervention Group) 249 (Control group)
Completed	242 (Intervention Group)	Participants who attended all three intervention sessions.	Completed all sessions	242
Not completed	7 (Intervention Group)	Participants dropped out before completing the 2nd and/or 3rd session.	Protocol violation	7

Period 2: Follow-up phase

This was a six-month post-intervention follow-up period, during which participants in the intervention group received periodic support visits to reinforce behavioral changes and sustain the practices introduced during the BCC sessions (Table 2).

Table 2. Overview of participation status and milestone achievements in follow-up phase

Participation status	Data (number of participants)	Comments	Milestone title	Milestone data (number of participants)
Started	242 (Intervention Group)	Participants who completed all the sessions of the intervention and entered follow-up phase.	Follow-up initiated and available at first follow-up visit	242

Completed	239 (Intervention Group)	Participants available at 6-month follow-up assessment.	Follow-up completed	239
Not completed	3 (Intervention Group)	Participants lost to follow-up during the periodic monitoring visits conducted every two months.	Lost to follow-up	3

Period 3: Post-intervention evaluation

This period represents the final stage of the study to assess the effectiveness of the BCC module on key menstrual health outcomes through a quasi-experimental design using matched control and intervention participants (1:1 PSM) (Table 3, Table 4A and 4B). Outcome assessments were done for dysmenorrhea, PMS and MI.

Table 3. Participant flow and milestone completion in post-intervention outcome evaluation before matching

Participation status	Outcomes	Data (number of participants)	Comments	Milestone title	Milestone data (number of participants)
Started	Dysmenorrhea, PMS and MI	239 (Intervention), 241 (Control)	Participants agreed to join and assessed for final evaluation of outcomes	Assessment initiated	480

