
Statistical Analysis Plan (SAP)

Statistical analysis overview

Statistical analyses were conducted to evaluate the impact of the BCC intervention on three binary outcomes: dysmenorrhea, PMS, and IMC. Categorical variables were summarized as frequencies and percentages and analyzed using the chi-square (χ^2) test. Continuous variables were presented as means with standard deviations and compared using independent t-tests. To adjust for potential baseline imbalances between the intervention and control groups, propensity score matching (PSM) was carried out using logistic regression. A 1:1 nearest-neighbor matching algorithm was applied with a caliper width of 0.01 and without replacement. Post-matching covariate balance was assessed using standardized mean differences (with a bias threshold of <10%) and chi-square tests. The primary analysis of intervention effects was conducted using conditional logistic regression on the matched sample. To validate the findings, bivariate and multivariate logistic regression analyses were also performed on the unmatched dataset. Additionally, sensitivity analyses were conducted to ensure the robustness and consistency of the results, including covariate balance diagnostics, estimation of the average treatment effect (ATE) and the average treatment effect on the treated (ATT), and Bayesian logistic regression on the matched sample.

Comparison group selection

1. Intervention Group (received BCC module)
2. Control Group (did not receive BCC module)

Type of statistical test: Superiority

- Comments: The analyses were designed to assess whether the BCC intervention group had superior outcomes compared to the control group using fixed-effect models on matched pairs. Power calculations were based on expected reductions in outcome prevalence.

Statistical test of hypothesis

Conditional logistic regression was used to estimate the odds of binary outcomes between intervention and control groups after matching.

- P-Value: < 0.05
- Comments (P-Value): A p-value < 0.05 was considered statistically significant. No adjustments for multiple comparisons were made. Results were considered statistically significant at $p < 0.05$.

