- Method: Chi-squared, t-test, regression (logistic), conditional logistic regression
- Comments (Method): Pre- and post-PSM tests used Pearson's chi-square; conditional logistic regression applied to matched data; bivariate and multivariate logistic regression used for robustness checks

Method of Estimation

- Estimation Parameter: Odds Ratio (OR)
- Estimated Values: Reported as crude odds ratios (COR) and adjusted odds ratios (AOR). Coefficient value was used to estimate ATE and ATT (Table 11).
- Confidence Interval Level: 95%
- Number of Sides: 2-sided
- Lower and upper limit: Reported per outcome (see Table 11)

- Parameter Dispersion Type: Standard error of the mean
- Estimation Comments: Odds ratios compared the intervention group (numerator) to the control group (reference) for menstrual outcomes. Odds ratios reflect the likelihood of menstrual outcomes in the intervention group relative to the control group. ATE and ATT were also estimated using PSM.

Table 11. Estimated odds ratios from bivariate and multivariable (before matching) as well as conditional (after matching) and logistic regression models assessing the impact of the BCC module on menstrual health outcomes

Outcomes	Before matching		After matching
	COR (95% CI)	AOR (95% CI)	AOR (95% CI)
Dysmenorrhea	0.07 (0.04, 0.11)***	0.13 (0.06, 0.26)***	0.13 (0.05, 0.34)***
Premenstrual syndrome	0.07 (0.04, 0.11)***	0.13 (0.07, 0.23)***	0.12 (0.06, 0.27)***
Menstrual Irregularity	0.12 (0.07, 0.20)***	0.26 (0.14, 0.48)***	0.21 (0.09, 0.45)***

* Indicated chi square value define the level of significance i.e. * $p < 0.05$, ** $p < 0.01$, *** $p < 0.001$

Other statistical analysis

Additional scientifically appropriate analyses were conducted to ensure robustness and validity of the findings:

1. **Propensity Score Matching (PSM):** PSM was used to control for baseline differences between the intervention and control groups. Participants were matched 1:1 using nearest-neighbor matching with a caliper width of 0.01 and without replacement. Covariate balance was assessed using standardized mean differences (bias <10%) and post-matching chi-square tests.

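### Women in the intervention arm were taught together in campus sessions by two educators, but no planned analysis allows for correlation among women taught together, so the intervals are too narrow if that correlation is positive

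*Combined protocol and SAP*

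**What the plan says.** **Delivery.** Under Group description, the protocol says: "The module consisted of three interactive sessions that included educational presentations, yoga demonstrations, informational pamphlet distribution, quiz competitions". Under Recruitment details: "University-approved session dates were held in campus venues". Under Period 1: "Two trained female educators facilitated these sessions". Three universities took part. The number of session groups, their size and the allocation of educators are not given.

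**Follow-up.** Under Period 2, "participants in the intervention group received periodic support visits to reinforce behavioral changes". Whether these visits were to groups or to individuals is not stated.

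**Control arm.** "The Control group consisted of female students from the same universities who were not exposed to the BCC intervention". Any session or educator effect can therefore arise in one arm only.

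**Analysis.** The SAP overview states: "The primary analysis of intervention effects was conducted using conditional logistic regression on the matched sample". The comment on the superiority test describes the analysis as "using fixed-effect models on matched pairs". Unmatched logistic regression, ATE/ATT and a Bayesian logistic model are supporting analyses. The SAP mentions no random effect, clustered variance, ICC or design effect. Session group, educator and university are absent from both matching lists under Baseline Measure Information, and Limitation and caveats does not mention clustering.

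**The concern.** Women who attend the same session share an educator, a date and a group dynamic, so their later outcomes may be more alike than those of women taught apart. Conditional logistic regression removes what the two members of a pair share. It does not deal with two treated women from one session who sit in different pairs: their common session effect makes those pairs correlated. This is a problem of variance, separate from confounding by campus, and adding campus to the matching would not remove correlation between women taught together within a campus.

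At stake is the stated precision of all three primary effects in Table 11 and of the ATE/ATT in Table 12.

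**Working it through.** **1. Reproduce the crude intervals.** Counts are from Table 10. The printed MI cells are misplaced. The row total of 323 equals 118 + 205, so I take irregular as 110 of 228 (control) and 23 of 228 (intervention). This gives 133/456 = 29.2%, the printed percentage.

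Formula: SE = √(1/a + 1/b + 1/c + 1/d), interval = OR × exp(±1.96 SE).

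| Outcome | Yes/no, intervention | Yes/no, control | Rebuilt OR (95% CI) | Printed |
|---|---|---|---|---|
| Dysmenorrhea | 75/159 | 209/29 | 0.0655 (0.041, 0.105) | 0.07 (0.04, 0.11) |
| PMS | 23/205 | 145/83 | 0.0642 (0.039, 0.107) | 0.07 (0.04, 0.11) |
| MI | 23/205 | 110/118 | 0.120 (0.073, 0.199) | 0.12 (0.07, 0.20) |

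All three intervals agree to two decimals with a formula that has no clustering allowance. (The PMS point estimate rounds to 0.06, not 0.07.) The adjusted, matched and ATE/ATT intervals cannot be rebuilt from printed data.

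**2. Assumptions.** The documents give no ICC and no group count. I assume 3, 6 or 10 session groups and a latent (logit-scale) ICC of 0.02 to 0.05, with clustering in the intervention arm only. The scale matters. With between-group variance σ² = ICC/(1 − ICC) × π²/3, the observed-scale ICC is the variance of the group proportions divided by p(1 − p), found by numerical integration. At about 10% prevalence (PMS and MI, intervention arm), latent 0.05 is about 0.016 observed, and observed 0.05 is about 0.14 latent. For dysmenorrhea (75/234 = 32%), latent 0.02 and 0.05 are about 0.014 and 0.035 observed. For PMS and MI, latent 0.02 is about 0.006.

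**3. Crude odds ratios.** SE factor = √(1 + f(m − 1)ICC), with observed-scale ICC. Here m is the group size and f = (1/a + 1/b)/SE² is the intervention arm's share of the variance: 0.33, 0.72 and 0.73. Ten groups give m of about 23, and three give 78 (dysmenorrhea) or 76.

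- Dysmenorrhea: √(1 + 0.33 × 22.4 × 0.014) ≈ 1.05, up to √(1 + 0.33 × 77 × 0.035) ≈ 1.38.
- PMS: √(1 + 0.72 × 21.8 × 0.006) ≈ 1.05, up to √(1 + 0.72 × 75 × 0.016) ≈ 1.37.
- MI: about 1.05 to 1.37 likewise.

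**4. Matched odds ratios.** I simulated 98 pairs (6,000 runs) with variation between pairs and a session-group effect in the treated member, at control prevalence 0.85/0.64/0.48 and OR 0.13/0.12/0.21. The spread of the estimated log OR was compared with the model SE.

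| Latent ICC | True SE above model SE | Coverage of nominal 95% |
|---|---|---|
| 0.02–0.05 | 1–15% | 92–96% |
| 0.10 (stress case) | 6–32% | 88–94% |

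The low end is no larger than the ordinary small-sample error of the formula.

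**5. Effect on the matched intervals.** SE = ln(upper/lower)/3.92, and the new interval is OR × exp(±1.96 × factor × SE).

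| Outcome | SE | Printed | Factor 1.15 | Factor 1.3 | Factor at which the interval reaches 1 |
|---|---|---|---|---|---|
| Dysmenorrhea | 0.489 | 0.05–0.34 | 0.043–0.391 | 0.04–0.45 | 4.17/1.96 = 2.13 |
| PMS | 0.384 | 0.06–0.27 | 0.051–0.285 | 0.05–0.32 | 5.53/1.96 = 2.82 |
| MI | 0.411 | 0.09–0.45 | 0.083–0.530 | 0.07–0.60 | 3.80/1.96 = 1.94 |

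The last column divides |ln(OR)|/SE by 1.96.

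**The case against.** The best reply is that almost everything needed to size the problem is missing. With no ICC, group count or group size, the documents do not prove that any interval is wrong. In the main scenarios the simulated coverage of the matched analysis, 92–96%, includes the nominal value. University effects common to both arms could also partly offset the session effect. The larger threats are bias: voluntary registration, and covariates recorded after the intervention. Wider intervals repair neither.

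This limits what can be claimed. Four stronger readings are tempting and unsupported:

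- A reader might infer that every printed interval has been shown to ignore clustering. That is checked only for the crude odds ratios. For the rest it is inferred from the methods named, and no variance estimator is stated for the ATE/ATT.
- A reader might infer that the printed intervals certainly fall short of 95% coverage. That needs a positive within-session correlation, which is plausible for interactive teaching but not documented.
- A reader might infer that the two-monthly support visits were also shared. Their format is not stated.
- A reader might infer that significance is lost. If the three universities were the only clusters, a t reference with 2 df (critical value 4.30) would exceed the z values for dysmenorrhea (4.17) and MI (3.80) even with no inflation. Nothing in the documents shows that there were only three groups, so this is a reason to report the number and not a result.

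The remedy also has a condition. Nothing says that a woman stayed in the same group for all three sessions, and two educators are too few to estimate an educator effect. What remains is that one-arm group teaching is documented and neither the analysis nor the limitations address it.

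**Conclusion.** The point holds as one about precision. Teaching was shared, in the intervention arm only, and no listed analysis allows for it. If women taught together are positively correlated, the intervals in Tables 11 and 12 are too narrow by an amount the documents cannot fix.

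Under the assumptions in the working, the matched SEs are understated by roughly 1–15% and the crude SEs by a factor of about 1.05–1.4. The matched intervals stay below 1 at inflation of 1.15 and of 1.3. With a normal critical value, the matched SE would have to be about 1.9 to 2.8 times the model value before an interval reached 1. The direction of effect is therefore not put in doubt by this point. The main uncertainty is the number of groups: if there were very few, a normal critical value would itself be too generous.

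**What to change.** 1. Report the number and size of session groups at each campus, how the two educators were allocated, and whether support visits were to groups or individuals.
2. If attendance lists show stable membership and there are enough groups, re-estimate the variance of the matched OR, COR, AOR, ATE and ATT allowing for session group in the intervention arm only. Use either a cluster-robust variance with a small-sample correction or a random session-group effect in that arm. In the matched data, each pair can be assigned to the session group of its treated member. State the method in the SAP overview and under Method of Estimation.
3. If membership was not recorded, was not stable, or the groups are too few, leave Table 11 as it is. Add a separate sensitivity table with intervals inflated over a stated ICC range on one named scale, labelled as assumed.
4. In the fallback case, name clustering under Limitation and caveats.

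The cost is a re-run on existing data plus SAP and table wording, with no new data collection. The downside is wider intervals, and an imprecise cluster variance if groups are few.
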